#### **6.4. Study Vaccine Compliance**

Study vaccine will be administered IM by blinded qualified study-site personnel at the study site. Details of each administration will be recorded in the eCRF (including date and time of injection, and site of administration). For blinding procedures, see Section 6.3.

#### **6.5. Dose Modification**

Not applicable.

#### **6.6. Continued Access to Study Vaccine After the End of the Study**

Participants will be instructed that study vaccine will not be made available to them after they have completed/discontinued study vaccination.

#### **6.7. Treatment of Overdose**

For this study, any dose of study vaccine greater than the protocol-specified dose will be considered an overdose. The sponsor does not recommend specific treatment for an overdose.

In the event of an overdose, the investigator or treating physician should:

- Contact the Medical Monitor immediately.
- Closely monitor the participant for AE/SAE/AESIs until resolution.
- Document the quantity of the excess dose in the eCRF.
- Report as a special reporting situation.

#### **6.8. Concomitant Therapy**

Prestudy therapies administered up to 30 days before vaccination must be recorded either during screening or on Day 1. Additionally, any history of SARS-CoV-2 vaccination (name/manufacturer of the vaccine and date of administration, whenever possible) prior to and during the study will be collected in the eCRF.

Concomitant therapies associated with solicited AEs will be collected by the participants in the participant diary from the time of study vaccination through 7 days after vaccination. Concomitant therapies associated with unsolicited AEs will be collected and recorded in the eCRF from the time of study vaccination through 28 days after vaccination. Concomitant therapies associated with SAEs or AESIs will be collected and recorded in the eCRF from ICF signature until 6 months after study vaccination.

Analgesic/antipyretic medications and non-steroidal anti-inflammatory drugs may be used post-vaccination only in cases of medical need (eg, fever or pain) and their use must be documented. Use of these medications as routine prophylaxis prior to study vaccination is discouraged.

Information on concomitant use of herbal supplements or vitamins will not be collected.

Use of any experimental medication (including experimental vaccines other than the study vaccine) during the study is not allowed.

Vaccination with licensed live attenuated vaccines within 28 days of a study vaccination (ie, before or after) is prohibited. Other licensed (not live) vaccines (eg, influenza, tetanus, hepatitis A, hepatitis B, rabies) should be given at least 14 days before (or at least 14 days after) administration of study vaccine in order to avoid potential confusion of adverse reactions and potential immune interference. If a vaccine is indicated in a post-exposure setting (eg, rabies or tetanus), it must take priority over the study vaccine.

For SARS-CoV-2 vaccines either licensed or available under Emergency Use Authorization: live attenuated vaccines should be given at least 28 days before or after vaccination; non-live vaccines should be given at least 14 days before or after vaccination. A viral-vectored SARS-CoV-2 vaccine is not to be given within 6 months prior to randomization or during the study period until 28 days after the last study vaccination.

Use of systemic corticosteroidsa must be documented throughout the study. Antineoplastic and immunomodulating agents administered parenterally, eg, cancer chemotherapeutic agents or systemic corticosteroids, or radiotherapy are prohibited throughout the study. If the use of systemic corticosteroids, antineoplastic or immunomodulating agents or any therapy described in Exclusion Criterion 7 becomes medically indicated during the study for any participant, the sponsor should be notified.

The sponsor must be notified in advance (or as soon as possible thereafter) of any instances in which prohibited therapies are administered.

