- r. Concomitant therapies will be collected from the time of study vaccination through 28 days post-vaccination when associated with an AE, and from ICF signature until 6 months after the last study vaccination when associated with an SAE or AESI.
- s. Any history of SARS-CoV-2 vaccination (name/manufacturer of the vaccine and date of administration, whenever possible) prior to and during the study will be collected in the eCRF.
- t. All COVID-19 cases will be collected for all participants for the duration of the study. COVID-19 cases reported by the participant will be reported in the eCRF by the investigator.

- u. Rulers and thermometers will be distributed at these visits.
- v. Participants will be contacted by telephone 2 to 4 days post-vaccination to remind them to fill in the participant diaries and to check that they are entering information correctly.

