## 2.2. Background

RSV is a negative-sense, single stranded RNA virus that belongs to the family of *Paramyxoviridae*. RSV is traditionally classified into 2 subtypes, RSV A and RSV B, which diverged approximately 350 years ago and are mainly based on antigenic variations in the RSV G protein (Pandya 2019). Adults infected with RSV usually experience mild, cold-like symptoms of upper respiratory tract infection and recover within 2 weeks. However, infection can progress to severe LRTD causing substantial morbidity and mortality in vulnerable populations, such as adults with underlying comorbidities and the elderly, ie, aged 60 years and older. In long-term care facilities, RSV is estimated to infect 5% to 10% of the residents per year with significant rates of pneumonia (10% to 20%) and death (2% to 5%) (Falsey 2000). In one epidemiology study of RSV burden, it was estimated that 11,000 elderly persons die annually of RSV in the United States (Thompson 2003). Despite this high disease burden, there are currently no licensed preventive vaccines against RSV infection.

To address this unmet medical need, the sponsor is developing the Ad26/protein preF RSV vaccine for use in adults, which is currently in clinical evaluation. This vaccine contains the combination

of an Ad26 viral vector expressing the RSV A2 preF protein (Ad26.RSV-A.preF) and the preF protein of RSV A2 (RSV-A preF protein). The F protein is highly similar between RSV A and B subtypes and its prefusion form has been shown to be immunogenic (Sullender 2000, Williams 2020). Antibodies against preF protein have also been suggested as correlates of protection for RSV (Mazur 2019). Results showed that the vaccine containing Ad26.RSV-A.preF and RSV-A preF protein components has a favorable reactogenicity profile as well as induced durable humoral and cellular immune responses (IB Ad26/protein preF RSV vaccine 2021). In a currently ongoing Phase 2b clinical study (VAC18193RSV2001), this vaccine has been shown to prevent RSV-mediated LRTD due to both RSV A and B infection. However, further exploratory analyses suggested that the observed VE against RSV B subtypes was lower compared to VE against RSV A subtypes. In case these findings would be confirmed in larger studies, there might be opportunity to identify possibilities to improve the VE of the current vaccine against RSV B subtypes.

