| PRIMARY                                                                                                                                                                                                                                     |                                                                                                                                                                                                                                                                                                                                                                                                                                                                                                                                                                                                                                                                                                                                                   |
| 
 
To assess immune responses, including durability to the selected RSV.preF-based vaccine formulation (formulation for future clinical development) in groups with and without revaccination
 
       | 
 
RSV neutralization antibody titers
 
                                                                                                                                                                                                                                                                                                                                                                                                                                                                                                                                                                                                                                                              |

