  7. received hematopoietic stem cell transplant in medical history, treatment with immunoglobulins expected to impact the vaccine-induced immune response (including monoclonal antibodies for chronic underlying conditions) in the 2 months, immunoglobulins specific to RSV, human metapneumovirus, or parainfluenza viruses in the 12 months, apheresis therapies in the 4 months, or blood products in the 4 months before the planned administration of the first study vaccine or has any plans to receive such treatment during the study.

*Note: Locally administered monoclonal antibodies (for example, intra-ocular) may be allowed upon sponsor approval. The investigator is encouraged to contact the sponsor to discuss eligibility of participants on immunoglobulin treatment.*

8. history of TTS or heparin-induced thrombocytopenia and thrombosis (HITT).
9. received or plans to receive:
  - a. Licensed live attenuated vaccines within 28 days before or after planned administration of study vaccination
  - b. Other licensed (not live) vaccines within 14 days before or after planned administration of study vaccination.
10. received or plans to receive a SARS-CoV-2 vaccine:
  - a. Live attenuated SARS-CoV-2 vaccine within 28 days before or after planned administration of the first or subsequent study vaccines.
  - b. Non-live SARS-CoV-2 vaccine within 14 days before or after planned administration of the first or subsequent study vaccines.
  - c. A viral-vectored SARS-CoV-2 vaccine within 6 months prior to randomization or during the study period until 28 days after the last study vaccination.
11. received an RSV vaccine in a previous RSV vaccine study at any time prior to randomization.
12. received or plans to receive an Ad26-vectored vaccine at any time prior to randomization until 28 days after the last study vaccination (for exclusion criteria related to SARS-CoV-2 vaccines; please refer to Exclusion Criterion 10).

- 
13. has taken any disallowed therapies as noted in Section 6.8, Concomitant Therapy, before vaccination.
  14. received an investigational drug or used an invasive investigational medical device within 30 days or received an investigational vaccine within 6 months before the planned administration of the study vaccine or is currently enrolled or plans to participate in another investigational study during this study.  
  

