**Table 2 – Analysis sets**

Analysis Sets	Description
All screened	This analysis set includes all participants screened for the study, regardless of whether they were screen failures or they got enrolled in the study. Rescreened participants are counted only once.
Randomized	The randomized analysis set includes all participants who were randomized in the study.
Full Analysis Set (FAS)	The full analysis set (FAS) will include all participants who received the study vaccine, regardless of the occurrence of protocol deviations. All safety and participant information analyses will be based on the FAS.
Per-protocol Immunogenicity (PPI) Set	The Per-protocol Immunogenicity (PPI) Set will include all randomized participants who received the planned study vaccine(s) and for whom immunogenicity data are available. Samples taken after a participant experiences a major protocol deviation expected to impact the immunogenicity outcomes will be excluded from the PPI analysis. The list of major protocol deviations that would lead to elimination from the immunogenicity analysis will be specified in the major protocol deviation criteria

Analysis Sets	Description
	document, which will be finalized before database lock and unblinding. The analysis of all immunogenicity endpoints will be based on the PPI Set. For key tables, sensitivity immunogenicity analyses might also be performed on the FAS.

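### The plan neither systematically records a non-study licensed RSV vaccine during the 3- to 5-year durability follow-up nor says how later titres are to be analysed

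*Protocol*

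**What the plan says.** **Endpoint.** The Cohort 4 primary objective is "To assess immune responses, including durability to the selected RSV.preF-based vaccine formulation (formulation for future clinical development) in groups with and without revaccination" (Protocol Section 3), with RSV neutralising titres as the endpoint. Durability is a secondary objective in Cohort 3 and an exploratory one in Cohorts 1 and 2. Follow-up runs 5 years in Cohort 4 and Arms 11a, 11b and 12, and 3 years in Cohorts 1 and 2.

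**What is barred.** Protocol 6.8 reads "Other licensed (not live) vaccines (eg, influenza, tetanus, hepatitis A, hepatitis B, rabies) should be given at least 14 days before" and continues "or at least 14 days after) administration of study vaccine". Exclusion criterion 9b sets the same window: "Other licensed (not live) vaccines within 14 days before or after planned administration of study vaccination". Live attenuated vaccines have a 28-day window. Criterion 12 bars Ad26-vectored vaccines until 28 days after the last study vaccination. Criterion 11, the only one that names RSV vaccines, covers a person who "received an RSV vaccine in a previous RSV vaccine study at any time prior to randomization". Experimental vaccines are barred throughout, but a licensed product is not experimental.

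**What is recorded.** Footnote r of the Schedule of Activities says "Concomitant therapies will be collected from the time of study vaccination through 28 days post-vaccination when associated with an AE", and extends this to 6 months after the last dose for SAEs and AESIs. Prestudy therapies cover the 30 days before vaccination. The schedule for the revaccination arms marks that row, and the eligibility rows, again at Visit 8 (Day X). SARS-CoV-2 is the only vaccination recorded for the whole study (footnote s).

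**How samples leave the analysis.** SAP Table 2: "Samples taken after a participant experiences a major protocol deviation expected to impact the immunogenicity outcomes will be excluded from the PPI analysis". The qualifying deviations are to be listed in a separate document. SAP 5.3.3 compares the combined durability arms at every timepoint and does not mention outside RSV vaccination.

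**Setting.** Protocol 2.2 states that "there are currently no licensed preventive vaccines against RSV infection".

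**The concern.** The rules fit the situation when the protocol was written, but the follow-up extends well beyond it. The protocol itself reports Phase 2b efficacy for one RSV vaccine and a Phase 3 trial under way, and it enrols adults aged 60 and over, some with heart or lung disease. That an RSV vaccine might be licensed and offered to them within 5 years is foreseeable.

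Such a vaccine would raise the very titres that measure durability. An arm in which some participants had taken it would appear to wane less than the study vaccine alone would allow. Without a record of who took it and when, the analyst could neither remove the affected samples nor run a sensitivity analysis.

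A related risk concerns Arms 12 and 16, which receive placebo on Day 1 and their first active dose at Day X, at least 12 months later. An unrecorded outside RSV vaccine in between would make that dose a second exposure.

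The protocol already applies this reasoning elsewhere. Criterion 7 excludes RSV-specific immunoglobulins, including planned use during the study, and 6.8 asks that the sponsor be told if such treatment becomes indicated.

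**Working it through.** **Step 1: does any existing rule reach the yearly visits?**

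- Bar on use: ends 14 days after a study vaccination for a non-live, non-Ad26 product, 28 days after for a live one, and 28 days after the last study vaccination for an Ad26-vectored one. In the revaccination arms that last limit falls 28 days after Day X.
- AE-linked recording: 28 days after vaccination.
- SAE- or AESI-linked recording: 6 months after the last vaccination.
- Day X checks: one visit, with a 30-day look-back for therapies.
- Yearly visits (Day 730 onward in the revaccination arms, Day 365 onward in Cohorts 1 and 2): none of the above is a routine question about RSV vaccination.
- Analysis rule: only the major-deviation rule, whose list is not in the protocol or SAP.

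**Step 2: reproduce the plan's durability figures.** Protocol 9.2.4 wants about 150 per arm at year 5 and assumes 10% dropout per year.

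- Linear loss: 150 / (1 − 5 × 0.10) = 300, the stated enrolment.
- Compound loss: 300 × 0.9^5 = 177 remaining, which is more favourable. I use 150, the plan's own target.

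The SD of 1.3 log2 (Protocol 9.2.2, RSV-A2, based on Day 29 data) also reproduces Table 14. With 55 per arm, t(108 df) × 1.3 × √(2/55) = 0.491 log2, giving 0.71 to 1.41 around a ratio of 1.

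**Step 3: precision at year 5**, assuming the same SD then.

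- One arm's GMT: 1.96 × 1.3 / √150 = 0.208 log2, or 1.16-fold.
- Ratio of two arms: 1.96 × 1.3 × √(2/150) = 0.294 log2, or 1.23-fold.

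**Step 4: inflation of one arm's GMT.** Assume that a fraction u has taken an outside RSV vaccine by the visit and that it multiplies their titre by a constant k. The mean log2 titre rises by u × log2(k), so the GMT is multiplied by k^u. Neither u nor k is in the documents, hence a range:

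| k | u = 5% | u = 10% | u = 20% |
|---|---|---|---|
| 2 | 1.04 | 1.07 | 1.15 |
| 4 | 1.07 | 1.15 | 1.32 |
| 8 | 1.11 | 1.23 | 1.52 |

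At k = 4 and u = 10% the shift is 0.20 log2, about the whole half-width of 0.208. Enrolling more participants narrows the interval but leaves the shift.

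**Step 5: the revaccination ratio** (11a+14 against 11b+15). With the same k in both arms the bias is k^(u1 − u2).

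- Equal uptake: k^0 = 1, no bias.
- 20% against 10%: 2^0.10 = 1.07, or 4^0.10 = 1.15.

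**Step 6: precision after excluding the affected samples.**

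- u = 10%: 150 falls to 135, half-width 1.16-fold.
- u = 20%: 150 falls to 120, half-width 1.18-fold.

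**The case against.** The other side has several fair points.

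- **The bar is not uniform.** A reader might infer that any licensed RSV vaccine is allowed from 14 days after the first dose. Criterion 12 contradicts that for Ad26-vectored products. The one RSV vaccine that the documents describe in late development is Ad26-based, and in the revaccination arms it is barred until 28 days after Day X. This narrows the gap but leaves open other non-live products and the later years of follow-up.
- **Some recording exists.** A reader might infer that an outside RSV vaccine would never be recorded. The AE- and SAE/AESI-linked entries and the Day X checks would catch some cases. They do not extend to the yearly visits.
- **The deviation list is unseen.** It could name outside RSV vaccination, so it cannot be said that the PPI rule would fail to remove such samples. Even then it could act only on cases that happened to become known.
- **The size is assumed.** This stands in full. With k = 2 the effects are modest.
- **Analyses are descriptive, arms are randomised, and participants and sites stay blinded.** This argues against assuming unequal uptake. It does not protect a single arm's GMT over time, which is what a durability estimate reports.
- **A field could be added by amendment once a product is licensed.** True, but any doses taken before the amendment would have to be reconstructed retrospectively.

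**Conclusion.** The point holds as a foreseeable gap in data capture and analysis, not as an internal contradiction. As written, the plan has no routine record of non-study RSV vaccination over the durability period and no rule for titres measured after it. Such samples would stay in the PPI analysis unless the deviation-criteria document lists the event and the case becomes known.

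The supported consequence is inflation of late GMTs. For assumed uptake of 10 to 20% and a 2- to 4-fold boost it is 1.07 to 1.32-fold, against a year-5 half-width of about 1.16-fold. This rests on an RSV vaccine being licensed and used during follow-up, on one constant boost, and on the Day 29 SD carrying over to year 5.

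A reader might also infer that the revaccination contrast will be diluted, for example because placebo recipients at Day X notice less reaction and seek the licensed vaccine more often. The documents do not support that as a finding: equal uptake and boost cancel from the ratio, and nothing shows that they would differ by arm. It remains a possibility that recorded data would let the sponsor check.

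The change should be made, because an analyst cannot later supply vaccination dates that were not collected.

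**What to change.** 1. In Protocol 6.8 and Schedule of Activities footnote s, add the recording of any non-study RSV vaccination (product and date) to study end in all cohorts. Use the form and contacts already in place for SARS-CoV-2 vaccination.
2. In the SAP (Table 2 and 5.3.3), pre-specify that immunogenicity samples taken after a non-study RSV vaccine are excluded from the PPI durability analysis, whether or not it counts as a protocol deviation. Commit to an FAS sensitivity analysis that includes them, and align the major-deviation criteria document.

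The cost is one eCRF item, one question at existing contacts and a short SAP rule. There are two statistical downsides. Fewer late samples enter the PPI analysis, though the loss of precision is small (step 6). Exclusion may also introduce selection, because people who seek vaccination may differ from those who do not. That is why both analyses should be reported.

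No change to criterion 11 is needed for this purpose, since that would alter eligibility. Whether to restrict outside RSV vaccination is a clinical decision for the sponsor.

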## 6.9. Study Pausing Rules

For Cohort 1, randomization and vaccination of participants will be suspended during review of the 24-hour data following the first administration of study vaccine to sentinel participants in each group (see Section 4.1).

If a study vaccination is considered to raise significant safety concerns (and a specific set of pausing criteria have been met), further vaccination of participants will be paused. The concerned data will be reviewed by the DRC, after which the DRC will recommend whether the pause can be lifted or not, or whether other steps are needed.

---

a Note: Ocular, topical, intra-articular or inhaled steroids are allowed.

The DRC will review blinded data first but has the right to request the randomization codes and review unblinded data if deemed necessary. The DRC will make recommendations regarding the continuation of the study to the sponsor study team. The sponsor study team will communicate conclusions regarding study continuation to the investigator, the Independent Ethics Committee (IEC) / Institutional Review Board (IRB), and applicable health authorities as appropriate.

After the first DRC meeting triggered by the occurrence of a given pausing rule, the DRC will convene thereafter for each additional participant meeting that pausing rule.

The occurrence of any of the following events will lead to a pause in further study vaccination. This list is only applicable for concerned AEs that occur up to 4 weeks after each vaccination and to concerned SAEs and AESIs.

1. Death of a participant, considered related to study vaccine or if the causal relationship to the study vaccine cannot be excluded; OR

Note: All cases of death will be sent for DRC information. Upon their review, DRC may then decide whether a study pause is required.

2. One or more participants per cohort experience an SAE, AESI (ie, confirmed TTS), or a Grade 4 (solicited or unsolicited) adverse event or a persistent (upon repeat testing) Grade 4 laboratory abnormality that is determined to be related to study vaccine (in Cohorts 1 and 2 only); OR
3. One or more participants per cohort experience anaphylaxis or generalized urticaria within 24 hours of vaccination, clearly not attributable to other causes than vaccination with study vaccine; OR
4. Two or more participants per cohort experience a Grade 3 or 4 unsolicited AE of the same type (as per medical judgment of the sponsor), that is determined to be related to study vaccine, that persists for 72 hours or longer; OR
5. Two or more participants per cohort (in Cohorts 1 and 2 only) experience a persistent (upon repeat testing) Grade 3 or 4 laboratory abnormality related to the same laboratory parameter and considered related to study vaccine, that persists for 72 hours or longer; OR
6. Two or more participants per cohort experience a Grade 3 or 4 solicited AE of the same type, determined to be related to study vaccine, that persists for 72 hours or longer.

For number 2 and number 5: to assess abnormal laboratory values, the test must be repeated at least once, within 48 hours of the site becoming aware of the abnormal value.

For number 4, number 5, and number 6: after each DRC review of similar AEs, the Committee will indicate the conditions under which it requires further notification and review of the subsequent similar AEs.

To enable prompt response to a situation that could trigger pausing rules, the investigator should notify the sponsor's medical monitor or designee (AND fax or email serious adverse event form to Global Medical Safety Operations, if applicable), immediately and no later than 24 hours after becoming aware of any related adverse event of Grade 3 or above AND update the eCRF with relevant information on the same day the adverse event information is collected. A thorough analysis of all Grade 3 (or above) cases will be carried out by the sponsor's medical monitor or designee, irrespective of whether the criteria for pausing the study are met. Based on the pausing criteria, the sponsor's medical monitor or designee then decides whether a study pause is warranted. All sites will be notified immediately in case of a study pause. The sponsor's medical monitor or designee is responsible for the immediate notification of DRC members and coordination of a DRC meeting in case of a study pause.

Vaccinations for an individual participant may be suspended for safety concerns other than those described in the pausing criteria, at the discretion of the investigator if he/she feels the participant's safety may be threatened. The sponsor's medical monitor or designee or the investigator(s) (upon consultation with the sponsor's medical monitor or designee) may initiate DRC review for any single event or combination of multiple events which, in their professional opinion, could jeopardize the safety of the participants or the reliability of the data.

Vaccinations for the study may be suspended for safety concerns other than those described above, or before pausing rules are met, if, in the judgment of the DRC, participant safety may be threatened.

Resumption of vaccinations paused by the DRC will start only upon receipt of written recommendations by the DRC. The clinical site(s) will be allowed to resume activities upon receipt of a written notification from the sponsor. The communications from the DRC will be forwarded by the investigator to the IRB/IEC and by the sponsor to the relevant health authorities, according to local standards and regulations.

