#### **8.3.1. Time Period and Frequency for Collecting Adverse Event, Serious Adverse Event and Adverse Event of Special Interest Information**

##### **All Adverse Events**

AEs and special reporting situations, whether serious or non-serious, that are related to study procedures or that are related to non-investigational sponsor products will be reported from the time a signed and dated ICF is obtained until the end of the study/early withdrawal.

Clinically relevant medical events not meeting the above criteria and occurring between signing of ICF and moment of first vaccination will be collected on the Medical History eCRF page as pre-existing conditions.

Solicited AEs, collected through a participant diary, will be recorded for each vaccination from the time of vaccination until 7 days post-vaccination.

All other unsolicited AEs and special reporting situations, whether serious or non-serious, will be reported for each vaccination from the time of vaccination until 28 days post-vaccination. Unsolicited AEs with the onset date outside the timeframe defined above (>28 days after previous study vaccination), which are ongoing on the day of the subsequent vaccination, should be recorded as such.

All SAEs and AEs leading to discontinuation from the study (regardless of the causal relationship) and all AESIs are to be reported from the moment of vaccination until 6 months post vaccination. The sponsor will evaluate any safety information that is spontaneously reported by an investigator beyond the time frame specified in the protocol.

All COVID-19 cases will be collected for all participants for the duration of the study.

See Section 7.2 for procedures associated with withdrawal of consent.

All AEs will be followed until resolution or until clinically stable.

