#### **Data Review Committee**

An internal DRC will be established to evaluate safety and reactogenicity data, including interim safety and reactogenicity data of Cohort 1, to ensure the continuing safety of the participants enrolled in this study. Ad-hoc meetings will be convened in case any of the pre-specified study vaccination pausing rules are met. This committee will consist of at least one medical expert in the relevant therapeutic area and at least one statistician; committee membership responsibilities, authorities, and procedures will be documented in its charter. After the review, the DRC will make recommendations regarding the continuation of the study.

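### The 24-hour notification that serves the pausing rules starts at Grade 3, so a non-serious Grade 1-2 generalized urticaria that meets rule 3 has no 24-hour route in the protocol text

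*Protocol*

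**What the plan says.** Section 6.9 of the protocol lists six events, each of which leads to a pause. Rule 3 is met when one or more participants in a cohort "experience anaphylaxis or generalized urticaria within 24 hours of vaccination, clearly not attributable to other causes than vaccination with study vaccine". It sets no grade and no seriousness condition.

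The same section then sets up the reporting step. Its purpose is stated first: "To enable prompt response to a situation that could trigger pausing rules, the investigator should notify" the sponsor's medical monitor or designee. The timing and scope follow: "no later than 24 hours after becoming aware of any related adverse event of Grade 3 or above", together with a same-day eCRF update. The next step has the same threshold: "A thorough analysis of all Grade 3 (or above) cases will be carried out" by the medical monitor, whether or not a pausing criterion is met. After that the "medical monitor or designee then decides whether a study pause is warranted".

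There is also a discretionary path. The medical monitor, or the investigator after consulting the medical monitor, "may initiate DRC review for any single event or combination of multiple events which, in their professional opinion", could endanger participants or the reliability of the data. Section 10.3.6 adds for the Data Review Committee (DRC): "Ad-hoc meetings will be convened in case any of the pre-specified study vaccination pausing rules are met". SAP Section 5.9.1 repeats this and adds no reporting route.

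**The concern.** The notification sentence exists to serve the pausing rules, but its threshold misses one of their triggers. Rule 3 acts on a single case, so any delay in reporting that case delays the pause by the same amount. Rules 4 to 6 need two participants and persistence for 72 hours or longer, yet every event that counts towards them carries the 24-hour notification.

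At stake is how soon vaccination stops at other sites after an early allergic-type reaction. Protocol Section 2.3.1 names urticaria as a possible allergic reaction to vaccination. The study is first-in-human for the RSV-B components and their combinations with the RSV-A components. Section 4.1 plans no enrolment pauses for safety in Cohorts 2, 3 and 4, which hold 528 + 400 + 540 = 1,468 of the 1,600 planned participants.

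**Working it through.** The plan gives no figure to reproduce. The check sets each pausing rule against the reporting routes that carry a 24-hour limit.

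**Routes with a 24-hour limit in the protocol**
- Section 6.9: related events of Grade 3 or above, to the medical monitor.
- Section 8.3.1: serious adverse events.
- Section 8.3.6: AESIs and potential AESIs, that is, TTS, thrombotic events and thrombocytopenia. Urticaria is not among them.

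**Rule by rule**

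| Rule | Trigger | 24-hour route |
|---|---|---|
| 1 | Death | Yes, as an SAE |
| 2 | SAE, AESI, Grade 4 event or Grade 4 laboratory finding | Yes, as SAE, AESI or Grade 3 or above |
| 3 | Anaphylaxis or generalized urticaria, any grade | In part |
| 4 | Grade 3-4 unsolicited event | Yes |
| 5 | Grade 3-4 laboratory abnormality | Yes; Section 10.4.1 counts these as adverse events |
| 6 | Grade 3-4 solicited event | Yes |

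Five of the six rules are fully covered. Rule 3 is the exception.

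**What remains inside rule 3.** Anaphylaxis would ordinarily be serious, as life-threatening or medically important. Urticaria judged medically important is an SAE too. Urticaria with an emergency-room visit or hospitalization is Grade 4 under Section 10.4.3. Grade 3 needs both loss of usual activity and medical intervention, in Section 10.4.3 and in the systemic illness row of Appendix 6; urticaria has no row of its own there. Widespread hives that do not stop usual activities therefore fall below Grade 3. The remaining class is non-serious Grade 1-2 generalized urticaria that the investigator clearly attributes to the vaccine.

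**How that class reaches the sponsor**
1. Urticaria is not one of the solicited diary terms in Section 8.3.2, so it is an ordinary unsolicited event. Section 8.3.1 says: "All other unsolicited AEs and special reporting situations, whether serious or non-serious, will be reported for each vaccination", over a 28-day window, with no hour limit on the report itself.
2. Section 10.3.9 asks for prompt eCRF completion after a visit, without a fixed deadline.
3. Section 6.9 permits the investigator to raise a DRC review, without a deadline or a duty to do so.
4. Section 6.8 asks for sponsor notification if systemic corticosteroids become medically indicated or a prohibited therapy is given, again without an hour limit. Cases treated in other ways do not fall under it.

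**Safeguards on detection.** The site may learn of a case at the 30-minute observation, at the diary call 2 to 4 days after vaccination, or at the Day 8 contact. With the +3-day window, that contact falls on Day 8 to Day 11, which is 7 to 10 days after a Day 1 vaccination. These contacts inform the site. They do not oblige it to tell the medical monitor.

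**Cohort 1.** The 4 + 12 + 6 + 4 = 26 sentinel participants have a 24-hour call and a review that includes sponsor physicians. The other 132 - 26 = 106 are covered by the 7-day reviews between groups and by the DRC review of Day 8 data before Cohort 2.

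**The case against.** Rule 3 is mandatory and every investigator holds the protocol. To judge a case clearly not due to other causes is to apply the pausing rule, so the investigator who does so knows that a pause is in play. The notification sentence states a purpose that excludes no rule. An investigator may reasonably class acute generalized urticaria as medically important in a first-in-human study, and a case treated with systemic corticosteroids goes to the sponsor under Section 6.8. The class left over is very small, no documented rate shows that even one case is to be expected, and site manuals, eCRF guidelines or the DRC charter may set tighter timing.

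Much of this stands. It limits the size of the point and holds the severity to minor. It does not remove the point, because the sentence is not silent: it states a threshold, and a site that follows it to the letter need not call within 24 hours for an event that meets a pausing rule. The duty to pause and to convene the DRC applies once the event is known to the person who decides, and neither duty gets the event to that person.

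A reader might infer that such a case has no route to the sponsor, or would be lost. The documents do not support that; the four routes above exist and lack only an hour limit. A reader might also subtract the sentinels, 1,600 - 26 = 1,574, and take the result as the number at risk. That figure only counts participants who are not sentinels. It ignores the later Cohort 1 reviews and says nothing about how many would have such an event.

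**Conclusion.** The point holds in a narrow form. In the protocol text, one class of event that meets rule 3 (non-serious Grade 1-2 generalized urticaria within 24 hours, clearly attributed to the vaccine) has no 24-hour route to the medical monitor. The consequence is a possible delay of a required pause, mainly in Cohorts 2 to 4. The delay cannot be quantified, because the documents give no urticaria rate, enrolment speed or eCRF entry time. No endpoint, analysis or pausing criterion is affected. Severity is minor.

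The conclusion assumes that the same-day eCRF update belongs to the Grade 3 sentence in which it stands. If it were read as covering all events, it would still be data entry and not a notification. The conclusion also concerns the protocol and SAP only; the site manuals were not available and could close the gap in practice, so an actual delay is not established.

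**What to change.** In Section 6.9, after the Grade 3 threshold in the notification sentence, add a second limb: *or any event, whatever its grade, that could meet a pausing rule, including every rule 3 event (anaphylaxis, or generalized urticaria, in the first 24 hours)*. Apply the same wording to the same-day eCRF update and to the medical monitor's case review. The pausing criteria and the role of the DRC stay as they are.

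The cost is one clause and a few extra site notifications. No new staff, committee or criterion is needed.
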